10.1.3 Part 2B Cohort Expansion

In Part 2B, approximately 40 participants will be treated in tumor-specific cohorts of HCC, CRPC, and TNBC, respectively.

This sample size will allow for a meaningful safety analyses assuming the incidence rate of drugrelated Grade 3-5 AEs within 24 weeks for historical ipilimumab 3 mg/kg in combination with nivolumab 1 mg/kg and is similar across the tumor types (see Section 5.5.6). A target of Grade 3-4 TRAE is considered to be clinically relevant in these patient populations.

Using a one group $\chi 2$ test with a 0.10 one-sided significance alpha level, a sample size of 40 participants per arm will have approximately 95% power to detect the difference between the Null hypothesis proportion of and the alternative proportion of $\chi = 0.10$.

This sample size will also provide reasonable power across the range of efficacy benchmarks cited in the Part 2B tumor types assuming an alpha level of 20% one-sided.

For the HCC protocol-defined population, the lowest ORR response value is predicted to be and the target ORR response is assumed to be

For the CRPC and TNBC protocol-defined populations, the lowest ORR response value is predicted to be and the target ORR response is assumed to be.

10.2 Populations for Analyses

For purposes of analysis, the populations are defined in Table 10.2-1.

Table 10.2-1: Populations for Analyses

Population	Description		
Enrolled	All participants who sign informed consent		
Randomized	All participants who are randomized to treatment arm (Part 2A)		
Treated	All participants who take at least 1 dose of study treatment		
Pharmacokinetic	All treated participants who have evaluable concentration-time data		
Immunogenicity	All treated participants who have baseline and at least 1 post-baseline pre-infusion immunogenicity assessment for the analyte evaluated		

Protocol Amendment No.: 09

Table 10.2-1: Populations for Analyses

Population	Description
Biomarker	All treated participants with available biomarker data.
Patient-reported outcome	All treated participants with patient-reported outcome data at baseline and at least 1 post-baseline assessment.

10.3 Statistical Analyses

The Statistical Analysis Plan will be developed, finalized, and signed before database lock. Below is a summary of planned statistical analyses of the primary and secondary endpoints. The final analysis is planned when all participants have successfully completed at least two post-baseline scans or discontinued early. Based on the post baseline scan assessment this is due approximately 6 months after the last participant first visit.

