2 SCHEDULE OF ACTIVITIES

Study assessments and procedures are shown in Table 2-1, Table 2-2, Table 2-3, Table 2-4, and Table 2-5.

In limited instances, scheduled events (including events other than safety assessments) can occur outside of the indicated timeframes but the Sponsor should first be notified.

If a participant has a delay in study treatment administration for any reason, then assessments and laboratory tests (with the exception of any tests needed to ensure participant safety) should be correspondingly delayed with the exception of tumor assessments. Tumor assessments continue per protocol schedule regardless of any treatment delay incurred.

The pharmacokinetic (PK), and safety profiles of BMS-986249 are being elucidated, modifications to the procedures (ie, reduction in PK, sampling, timing of procedures, dose schedules) currently outlined in Section 2 and Section 9 may be required. These modifications will not include the addition of new procedures and will be documented in a note to file or administrative letter.

In the event that multiple procedures are required at a single time point, the electrocardiogram (ECG) may be obtained up to 15 minutes earlier, vital signs may be obtained up to 10 minutes earlier or later, and clinical laboratory samples may be obtained up to 5 minutes earlier than the nominal time point, ensuring the PK samples can be collected on time.

 Table 2-1:
 Screening Schedule of Activities for All Study Parts

Procedure	Screening Visit (Days -30 to -1)	Notes					
Eligibility Assessments							
Informed Consent	X	Must be obtained prior to performing any screening procedures. A participant is considered enrolled only when a protocol-specific ICF is signed.					
Contact IRT	X	After the participants meet all eligibility criteria, sites will use IRT for participant number assignment. Register in IRT to obtain participant number. Subsequent visits will be registered into the IRT system for drug supply. See Section 5.1.1. If the IRT system is not available, participants will be enrolled manually. The participant number will be created in the IRT system upon availability.					
Inclusion/Exclusion Criteria	X	Must be confirmed prior to randomization/treatment assignment. See Section 6.1 and Section 6.2.					
Medical History	X	All medical history relevant to the disease under study. Include any toxicities or allergies related to previous treatments.					
Prior Cancer Therapies	X						

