Variable: Treatment Related AE with CTCAE Grade 3 or higher that occurred within 24 weeks from first dose Intercurrent events: early discontinuation of study

Treatment Policy: Patients that discontinue treatment early will have a 100 days post last dose safety follow-up. AEs occurring after this safety follow-up window will not be included in the analysis, even if they occurred within the 24 weeks from first dose.

Intercurrent event: initiation of subsequent anti-cancer therapy

While on treatment: Patients that initiate an anti-cancer subsequent therapy will be discontinued from study but will be followed up for safety events 100 days from last dose. Safety events regardless of whether they occur before or after subsequent therapy will be include in the analysis. AEs occurring past 100 days safety follow-up will not be included in the analysis, even if they occurred within the 24 weeks from first dose.

Intercurrent event: death and withdrew

While on treatment: Patients who die or withdraw consent before reaching the 24 weeks landmark will be included in the analysis and their Grade 3 to 5 treatment related AEs will be include in the summary.

Population level summary: Grade 3 to 5 treatment related adverse event incidence rate, comparison of Arm C vs Arm D and Arm F vs Arm D with estimated difference and odd ratio and 80% confidence interval using Cochran Mantel Haenszel methodology adjusting for stratification factors will be computed. Adjusted and unadjusted chi square test will be performed and p-values will be provided.

Objective	Endpoint
Primary	Primary
To evaluate the preliminary efficacy of BMS-986249 in combination with nivolumab (Arm C and Arm F) relative to historic nivolumab monotherapy data in participants with previously untreated, unresectable or metastatic melanoma	ORR as assessed by investigator using RECIST v1.1

Main Estimand for the Primary Objective

Treatment: 1200 mg BMS-986249 IV Q8W + 480 mg nivolumab IV Q4W (Arm C); 3 mg/kg ipilimumab Q3W + 1 mg/kg nivolumab IV Q3W for 4 doses followed three weeks later by 480 mg nivolumab IV Q4W(Arm D); 600 mg BMS-986249 IV Q4W + 480 mg nivolumab IV Q4W (Arm F)

Population: All treated participants with evaluable baseline tumor assessment per RECIST v1.1

Variable: BOR, defined as the best response, as determined by investigator, per RECIST 1.1

Intercurrent events: early discontinuation of study

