5.1.1 Screening Period

The screening period will be up to 30 days and begins by establishing the participant's initial eligibility and signing of the informed consent form (ICF). The screening assessments are shown in Table 2-1. If a participant exceeds the 30-day screening period due to a study-related procedure (eg, scheduling of a tumor biopsy or waiting for a study-related laboratory value), the participant must be re-consented and will require a new participant identification number. In this situation, the fewest number of procedures from the initial screening should be repeated to qualify the participant, while maintaining participant safety and eligibility. For Part 2A participants awaiting PD-L1 results, the screening window may be extended past the 30-day period upon discussion with the Medical Monitor (or designee). However, if screening extends over a prolonged period, baseline procedures, such as tumor assessments and labs, may need to be repeated so that they fall within the acceptable protocol-specified window. Within a given disease type, participants meeting all eligibility criteria will be enrolled in the study according to the part and treatment arm availability.

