5.3 End of Study Definition

The start of the study is defined as the first visit for the first participant screened. Similarly, the end of the study is defined as the last visit or scheduled procedure shown in Section 2 for the last participant. Primary study completion is defined as the final date on which data for the primary endpoint are expected to be collected.

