The final analysis will take place when all randomized participants have completed at least 36 weeks follow-up or discontinue earlier. Due to exploratory nature of the proof of concept (PoC) design, no multiplicity adjustment will be made for testing multiple endpoints or multiple treatment arms.

10.1.2.2 Changes to Sample Size Assumptions for Revised Protocol 07

[figure not shown]
The original sample size calculation was based on a 60% two-sided CI of ORR for the difference between treatments and required 54 participants per arm. As participants in Arm E will not be randomized as originally planned, the efficacy evaluation and the statistical comparison will use a reference value of based on nivolumab monotherapy historical data in melanoma (see Section 5.4.7.2).

One of the main objectives of this study is to evaluate the preliminary safety and tolerability of BMS-986249 in combination with nivolumab (Part 2A Arm C and Arm F).

Based on final analysis of CA209511, the ipilimimab 3 mg/kg in combination with nivolumab 1 mg/kg, the incidence rate of drug-related Grade 3-5 AEs within 24 weeks is estimated to be relative improvement in the incidence of Grade 3-5 TRAEs is considered to be clinically relevant.

Using a two group $\chi 2$ test with a 0.10 one-sided significance alpha level, assuming a 1:1 randomization ratio of experimental BMS-986249 in combination with nivolumab containing regimen to control ipilimumab in combination with nivolumab, a sample size of 60 participants per arm will have approximately 70% power to detect a ratio in favor of the alternative hypothesis of compared to the null hypothesis proportion of

The null hypothesis is the ratio of proportions above or equal to 1, the alternative hypothesis is the ratio of proportion is below to 1.

Protocol Amendment No.: 09 Date: 14-Mar-2023

e: 14-Mar-2023

The final analysis will take place when all randomized participants have completed at least 36 weeks follow-up or discontinue earlier. Due to exploratory nature of the PoC design, no multiplicity adjustment will be made for testing multiple endpoints or multiple treatment arms.

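### The final-analysis trigger in Section 10.3 has no 24-week minimum for the primary safety endpoint, and for Part 2A its 6-month forecast does not fit the 36-week rule

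*Combined protocol and SAP*

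**What the plan says.** Section 10.3 gives one trigger for the whole study: "The final analysis is planned when all participants have successfully completed at least two post-baseline scans or discontinued early". It adds a forecast: "Based on the post baseline scan assessment this is due approximately 6 months after the last participant first visit".

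For Part 2A only, Sections 10.1.2.1 and 10.1.2.2 both carry a different rule: "The final analysis will take place when all randomized participants have completed at least 36 weeks follow-up or discontinue earlier". Section 10.1.2.2 holds the current sample-size assumptions, so this is live text. Neither section says from what date the 36 weeks run.

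The primary safety estimand is the same in Table 4-4 (Part 2A) and Table 4-5 (Part 2B): "Variable: Treatment Related AE with CTCAE Grade 3 or higher that occurred within 24 weeks from first dose".

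Three other places bear on the timing:

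- Section 5.3 says "The start of the study is defined as the first visit for the first participant screened", which uses *first visit* for screening. It also says "Primary study completion is defined as the final date on which data for the primary endpoint are expected to be collected", but Section 10.3 does not tie the final analysis to that date.
- Section 5.1.1 allows up to 30 days of screening. For Part 2A participants awaiting PD-L1 results, "the screening window may be extended past the 30-day period" after discussion with the Medical Monitor.
- Section 10.3 calls itself a summary and defers to a Statistical Analysis Plan to be signed before database lock. The text of that plan is not in the document supplied.

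**The concern.** An endpoint with a fixed 24-week window needs every participant either to have passed Week 24 or to have a defined reason for stopping short. A trigger built on scans alone does not ensure this. The estimand tables say how to treat death and withdrawal before Week 24, but not a data cut before Week 24. A late enrollee without an event at the cut would simply count as event-free, so any bias in the incidence rate is downward.

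Part 2A also has two stated timings for one final analysis, and they are months apart. The choice affects the primary response endpoint too. Table 4-4 counts only confirmed responses, and Section 9.1.1 requires confirmation at least 4 weeks later. A response first seen at the Week 20 scan cannot be confirmed if the data are cut straight after that scan.

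**Working it through.** **Inputs.** Part 2A scans: Week 12 (±7 days) from first dose, then 8 weeks (±7 days) after the first scan (Tables 2-2 to 2-4). Part 2B scans: every 8 weeks (±7 days) from first dose (Table 2-4). Screening: up to 30 days. Safety follow-up: 100 days after last dose. One month = 30.44 days.

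**1. Reproduce the 6 months.**
- Part 2A from a screening visit 30 days before first dose: 30 + 140 = 170 days = 5.6 months at nominal dates, and 30 + 154 = 184 days = 6.0 months at the latest in-window dates. This matches the stated figure.
- Part 2A from first dose: 140 to 154 days = 4.6 to 5.1 months.
- Part 2B from screening: 142 to 149 days = 4.7 to 4.9 months.

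The forecast is reproduced only for Part 2A, counted from screening, with the full 30 days used.

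**2. When the two-scan condition can be met, from first dose.**
- Part 2A: 12 + 8 = Week 20 (18 to 22), nominally 4 weeks before Week 24.
- Part 2B: Week 16 (15 to 17), nominally 8 weeks before.

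**3. Does the forecast cover Week 24?** Six months = 182.6 days = 26.1 weeks.
- First visit means first dose: Week 26.1, no shortfall.
- First visit means screening, 30 days earlier: (182.6 − 30)/7 = Week 21.8, which is 2.2 weeks short.
- Break-even gap between first visit and first dose: 182.6 − 168 = 14.6 days.

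**4. The 36-week rule.** 36 weeks = 252 days = 8.3 months from first dose, or 282 days = 9.3 months from a screening visit 30 days earlier. Against the forecast it is later by 36 − 26.1 = 9.9 weeks or 36 − 21.8 = 14.2 weeks.

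**5. Early discontinuation.** 100 days = 14.3 weeks, and 24 − 14.3 = 9.7. If the phrase covered stopping treatment, someone who stopped after Week 9.7 would satisfy the trigger while safety follow-up still ran to Week 24 or later.

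**6. Size of the bias.** The accrual rate is not given and the design event rates are redacted, so these are assumptions: uniform accrual over 66.3 to 104 weeks and a true rate of 30-60%. The lower accrual figure is the interval from Revised Protocol 07 (15-Nov-2020) to Amendment 08 (22-Feb-2022), 464 days. Revised Protocol 07 defined Part 2B as well as the current Part 2A, so the same minimum is used for both. The formula, with events spread evenly over the window, is: points lost = (weeks short / accrual weeks) × (mean weeks missed / 24) × rate.

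| Cut | Share still inside window | Events missed | Points lost |
|---|---|---|---|
| 2A, strict two-scan (4 weeks short) | 3.8-6.0% | × 2/24 = 0.32-0.50% | 0.10-0.30 |
| 2B, strict two-scan (8 weeks short) | 7.7-12.1% | × 4/24 = 1.28-2.01% | 0.38-1.2 |
| Either part, Week 21.8 (2.2 weeks short) | 2.1-3.3% | × 1.1/24 = 0.10-0.15% | 0.03-0.09 |

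Section 5.5.1.3 reports that most ipilimumab immune-related events come within 12 weeks. If 80-90% of events fall by Week 12 and the rest are even over Weeks 12-24, the strict-cut loss is share × (10-20%) × 2/12 × rate = 0.02-0.12 points in Part 2A, and share × (10-20%) × 4/12 × rate = 0.08-0.48 points in Part 2B.

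For scale, the 80% CI half-width at n = 40 and a 50% rate is 1.2816 × √(0.25/40) = 10.1 points.

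**The case against.** Several points on the other side stand.

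- **Part 2A has a floor if the 36-week sentence governs.** Thirty-six weeks exceeds 24. The outright absence of a minimum is therefore a Part 2B matter; in Part 2A the problem is which text applies.
- **A reader might infer that the two Part 2A rules are incompatible.** They are not, as conditions. Both are minimums, and a cut at Week 36 would meet both. The misfit is between the 36-week rule and the 6-month sentence, which is a forecast.
- **A reader might infer that the cut will fall before Week 24.** The documents do not establish that. The Week 21.8 figure uses the maximum ordinary screening period. *Last participant first visit* is not defined, and with first dose within about 15 days of it the forecast date covers the window.
- **A reader might take early discontinuation to mean stopping treatment.** Sections 8.1, 8.2 and 8.2.1 point the other way: participants who ask to stop treatment stay in the study, and stopping is not treated as withdrawal. Some ambiguity remains because Table 4-4 names discontinuation of study as the intercurrent event and then describes patients who stop treatment.
- **A reader might argue that Part 2B matters more because its rate is tested against a fixed value.** The one-group test appears only in the sample-size text of Section 10.1.3. Table 4-5 and Table 10.3.2-1 plan an incidence rate with a confidence interval.

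The signed analysis plan could also settle the cut-off. That does not remove two ill-fitting timings from the current protocol text.

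**Conclusion.** The point holds in limited form. Read literally, Section 10.3 permits a final analysis before the 24-week primary safety window has closed for the last enrollees. Part 2B has no stated minimum, and the Part 2A 36-week rule does not fit the 6-month forecast.

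The shortfall is permitted by the wording, not certain, and the documents do not support a claim of material bias. Under the assumptions above, the downward bias is at most about 0.3 points in Part 2A and 1.2 points in Part 2B at a strict two-scan cut with even onset. It is less with early onset, and at most about 0.09 points at the Week 21.8 cut. The loss scales inversely with accrual time, so a cohort that filled faster than 66 weeks would lose proportionally more. Because the trigger waits for all participants, the part or cohort that finishes accrual last bears the loss.

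The case for changing the text is clarity about a primary endpoint and about when response is read, at almost no cost.

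**What to change.** 1. In Section 10.3, add to the trigger that every treated participant has reached at least 24 weeks from first dose, or has died, withdrawn consent, been lost to follow-up, or completed the 100-day safety follow-up. This also replaces the undefined early-discontinuation wording.
2. State one Part 2A trigger, with its start point, in Sections 10.1.2.2 and 10.3. The choice is the sponsor's. Keeping 36 weeks from first dose satisfies the floor and lets a response first seen at Week 20 be confirmed at the scheduled Week 28 scan. Keeping the two-scan rule requires the floor and removal of the 36-week sentence.
3. Label the 6-month sentence as an estimate and say whether first visit means screening or first dose, or delete it.

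The cost is text edits, with no added participants, visits or procedures. The data cut may move later. Against the forecast, the move is 0 to 2.2 weeks for the 24-week floor, or about 10 to 14 weeks if Part 2A keeps 36 weeks. Against a strict two-scan cut, the floor adds 4 weeks in Part 2A and 8 weeks in Part 2B.

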10.3.1 Analyses

The Part 2A efficacy analyses will be performed on the randomized population, with supplemental analyses on the treated population, while the efficacy analysis of Part 2B will be performed on the treated population (Table 10.3.1-1). The efficacy and safety analysis for Part 2B will be evaluated by tumor-specific cohort. Analysis of the treated participants from Part 1 will be presented separately. The following censoring rules will be applied for the definition of PFS and DoR:

- Subjects who did not progress or die will be censored on the date of their last evaluable tumor assessment.
- Subjects who did not have any evaluable on study tumor assessments and did not die will be censored on their date of randomization (for Part 2A) or first dosing (Part 1 and Part 2B).
- Subjects who receive subsequent anti-cancer therapy prior to documented progression or death will be censored at the date of the last evaluable tumor assessment conducted on or prior to the date of initiation of the subsequent anti-cancer therapy.

Additional details of the calculation of time-to-event endpoints such as DOR and PFS will be described in the Statistical Analysis Plan.

The efficacy and safety data from participants randomized in Part 2A Arms A, B, and E before Revised Protocol 07 will be analyzed using descriptive measures only.

Table 10.3.1-1: Efficacy - Statistical Analyses^a

Endpoint	Statistical Analysis Methods
Best observed response (BOR) BOR for a participant will be assessed per RECIST v1.1 or PCWG3 by investigator, unless otherwise specified	Summary and listing of BOR

Protocol Amendment No.: 09

Table 10.3.1-1: Efficacy - Statistical Analyses^a

Endpoint	Statistical Analysis Methods
ORR ORR is defined as the proportion of participants whose BOR is either CR or PR per RECIST v1.1 in the population of interest or PCWG3 for participants with prostate cancer.	Point estimate and CI by arm/cohort in Parts 2A and 2B Part 2A: Chi square test and sensitivity analysis using Cochran-Mantel-Haenszel test with the stratification factors as strata
DOR DOR for a participant with a BOR of CR or PR is defined as the time between the date of first response and the date of the first objectively documented tumor progression per RECIST v1.1 or PCWG3 or death, whichever occurs first.	Median and CI by K-M method for participants who responded, by arm/cohort
PFS PFS for a participant is defined as the time from the first dosing date (Part 1, Part 2B) or randomization date (Part 2A) to the date of first objectively documented disease progression per RECIST v1.1 or PCWG3 or death due to any cause, whichever occurs first.	Median and CI by K-M method and PFS rates
PSA Response Rate (For Part 2B CRPC Participants Only) Decrease in the level of PSA of at least 50% from baseline maintained for at least 3 weeks	Point estimate and CI
TTR TTR is defined as the time from the first dosing date (Part 1, Part 2B) or randomization date (Part 2A) to the date of the first confirmed response (CR or PR) per RECIST v1.1 or PCWG3.	Summary statistics for TTR
OS OS is defined as the time from enrollment (Part1, Part 2B) or randomization (Part 2A) to the date of death from any cause	Median and CI by K-M method (including OS rates, for example at 1 year and 2 years)

Abbreviations: BOR = best overall response; CI = confidence interval; CR = complete response; DOR = duration of response; K-M = Kaplan Meier; ORR = Objective Response Rate; OS = overall survival; PCWG3 = Prostate Cancer Working Group 3; PFS = progression-free survival; PR = partial response; PSA = prostate-specific antigen; RECIST = Response Evaluation Criteria in Solid Tumors; TTR = time to response.

Protocol Amendment No.: 09

^a Efficacy analyses will be executed with a 60% two-sided CI.

